### *Surgical Quality*

Frequency and percentage will be used to report grade 3-4 bleeding events during surgery and positive margins after surgery, separately. A 90% binomial confidence interval will be estimated for these events as well. All eligible and surgery treated patients will be analyzed. For any targeted event (bleeding or positive margins), if the lower limit of the 90% CI is above the expected rate, transoral resection surgery is deemed infeasible for future study.

An interim analysis was planned in the original design for grade 3-4 bleeding and Positive Margins. It was expected 3% of patients will experience grade 3-4 bleeding during surgery (requiring hemostasis in the operating room). It was anticipated 5% of patients with transoral surgery would have positive margins. Among the first 59 eligible patients who have completed transoral resection, had data submitted, and the surgical results are known, the percentage would be deemed too high if 13 (22%) or more patients are reported with grade 3-4 bleeding in the operating room or with positive margins. An interim analysis was performed for the Fall 2015 DSMC meeting. Among the first 59 patients with surgical data submitted in iMedidata Rave (59th patients registered on January 15, 2015), 5 grade 3 bleeding events and 2 positive margins were reported (total 7 events), and among the 10 patient who entered prior to January 15, 2015 with no surgical data, no bleeding event was reported. Based on results from the interim analysis, the specified stopping rule was not met.

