5.1.5.6 Pathologic assessment of extracapsular extension (ECE): Lymph nodes  $\leq$  2 cm in greatest dimension are considered adequately assessed with one section. Multiple lymph nodes  $\leq$  2 cm in greatest dimension may be submitted in a single cassette. Lymph nodes > 2 cm in greatest dimension require multiple sections (and possibly multiple cassettes); specifically, one section per 1 cm should be submitted. Sections should include the edge of the lymph node that interfaces with surrounding fibroadipose tissue.

5.1.5.7 Ligation of arterial blood supply of the primary oropharyngeal tumor is required to avoid major postoperative pharyngeal hemorrhage.

- At a minimum, it is recommended that the surgeon ligate the ipsilateral lingual and facial arteries. At the surgeon's discretion and judgment, ligation of other arteries, such as the ascending pharyngeal and superior thyroid, may be considered.
- If the external carotid arterial trunk itself is ligated, the surgeon must ligate the vessel at an adequate distance from the carotid bulb to avoid injury to the internal carotid artery. Care should be taken to avoid injuring the internal carotid artery if ligating the ascending pharyngeal artery, since its takeoff may occur posteriorly putting the ICA at risk.
- The attending surgeon is directed to perform this portion of the procedure him/herself.
- The arteries should be ligated but not divided.
- The case report form will now require the documentation, taken from the operative report, confirming that arterial ligation was performed and delineating which vessels were ligated.
- Please contact the study chair, [name], with any questions or to clarify.

Rev. 6/14

Rev. 1/16  
Rev. 9/16  
Rev. Add8

Failure to perform arterial ligation, and provide written documentation of this critical aspect of the surgery, will constitute a reportable deviation which will be forwarded to the Credentialing Committee and subject to peer-review and appropriate action. Such action may include suspension of the surgeon's credentials for involvement in the trial, thus preventing further accrual to the trial.

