#### 5.1.6.4 Surgical Protocol Compliance Criteria

Deviations Minor:

- "Close" margin, (< 3mm)
- suboptimal neck dissection (< 20 nodes removed)

Deviations Unacceptable: Those deviations that affect patient safety/outcome, which will result in an institution being suspended from further participation in the study, such as:

- Positive Margin rate exceeding 20% (assessed every 5 cases accrued)
- Inadequate nodal dissection (< 15 nodes removed)

Rev. 2/14

- Postoperative bleeding requiring return to the operating room for control, exceeding 20% of submitted patients (assessed every 5 patients accrued)

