
a This includes all deaths within 30 days of the last dose of treatment regardless of attribution. NOTE: Any death that occurs > 30 days after the last dose of treatment and is attributed possibly, probably, or definitely to the treatment must be reported within 7 calendar days of learning of the event.
 
b Protocol-specific expedited reporting requirements: The adverse events listed below also require expedited reporting for this trial:
 
Serious Events: Any event following treatment that results in persistent or significant disabilities/incapacities, congenital anomalies, or birth defects must be reported via CTEP-AERS within 7 calendar days of learning of the event. For instructions on how to specifically report these events via CTEP-AERS, please contact the AEMD Help Desk at [contact] or [contact]. This will need to be discussed on a case-by-case basis.
 
Bleeding: Any grade 3-4 bleeding (requiring hemostasis in the operating room), regardless of attribution or expectedness, must be reported via CTEP-AERS within 7 calendar days of learning of the event.
					

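### The surgical-feasibility rule counts only grade 3-4 bleeding, so a fatal bleed falls outside it, and the protocol's sections disagree on whether postoperative bleeds count

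*Combined protocol and SAP*

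**What the plan says.** Section 9.4 (Surgical Quality) defines what is reported at the end: "Frequency and percentage will be used to report grade 3-4 bleeding events during surgery and positive margins after surgery, separately". The population is broad: "All eligible and surgery treated patients will be analyzed". The decision is binding for each event type: "if the lower limit of the 90% CI is above the expected rate, transoral resection surgery is deemed infeasible for future study". The reference rates are in the same section: "It was expected 3% of patients will experience grade 3-4 bleeding during surgery (requiring hemostasis in the operating room") for bleeding, and "It was anticipated 5% of patients with transoral surgery would have positive margins". The interim rule in 9.4 combines the two events (13 or more of the first 59 patients) and places the bleeding in the operating room.

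The decision table in 9.1 gives the same interim rule as grade 3-4 bleeding or positive margins, with no limit on when the bleed occurs.

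Three other places bear on the definition:

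- Section 5.1.5.7: arterial ligation "is required to avoid major postoperative pharyngeal hemorrhage".
- Section 5.1.6.4, among the deviations that suspend an institution: "Postoperative bleeding requiring return to the operating room for control, exceeding 20% of submitted patients", assessed every 5 patients.
- Section 5.2.6, footnote b, expedited reporting: "Any grade 3-4 bleeding (requiring hemostasis in the operating room), regardless of attribution or expectedness", with no timing limit.

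Section 5.2.6 lists grade 5 in columns separate from grade 4, and toxicity is graded by CTCAE version 4.0 (5.3 and 9.5).

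**The concern.** A feasibility endpoint for an operation should count the worst outcome of the hazard it measures. Here the grade range has a ceiling. A bleed recorded as grade 5 is not grade 3-4, so under the stated rule the patient enters the denominator as having had no event. Reporting the death through the safety system does not change that, because no section carries those reports into the 9.4 count.

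Timing is a second problem. Sections 5.1.5.7 and 5.1.6.4 show that the protocol regards bleeding after the operation as a hazard to be prevented and policed, yet the sentence governing the final analysis refers to bleeding during surgery. Two analysts working from 9.1 and 9.4 could count different events for the same patients. At stake is a primary conclusion: whether transoral surgery is declared infeasible for a future study.

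**Working it through.** **1. Grade and timing, side by side**

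| Place | Grades named | Timing |
|---|---|---|
| 9.1 table, interim rule | 3-4 | none stated |
| 9.4, final reporting sentence | 3-4 | during surgery |
| 9.4, expected rate of 3% | 3-4 | during surgery, with a parenthesis requiring hemostasis in the operating room |
| 9.4, interim rule | 3-4 | in the operating room |
| 9.4, interim result | 5 events, all grade 3 | none stated |
| 5.2.6 footnote b | 3-4 | none stated; same operating-room parenthesis |
| 5.1.6.4, institution rule | none | postoperative, with return to the operating room |

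No statement of the feasibility rule names grade 5. The timing column does not agree with itself.

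**2. The plan's own figures**

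13/59 = 22.0%, as stated. The interim result is 5 + 2 = 7 events, below 13, so the interim rule was not met, as stated.

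**3. Where the final rule turns**

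Inputs: reference rate 3% (9.4) and a two-sided 90% binomial interval (9.4). Section 9.4 does not name the interval method; I assume the exact (Clopper-Pearson) interval, which 9.3 specifies for PFS. The number of eligible, surgery-treated patients is not stated. I bracket it with 515 (the accrual goal, an upper bound) and 376 (the patients expected to be evaluable on Step 2).

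For x events in n patients the lower limit L is the 5th percentile of a Beta(x, n - x + 1) distribution. The rule is met when L > 0.03.

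| x / n | Rate | Lower 90% limit | Rule met? |
|---|---|---|---|
| 22/515 | 4.27% | 2.91% | no |
| 23/515 | 4.47% | 3.07% | yes |
| 17/376 | 4.52% | 2.90% | no |
| 18/376 | 4.79% | 3.12% | yes |

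At 3%, 515 patients would give about 0.03 × 515 = 15 events, so the threshold lies about 8 events above expectation. With 376 patients, 0.03 × 376 = 11, and the threshold is about 7 above.

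**4. Sensitivity to bleeds left out (assumed rates)**

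The documents give no rate for postoperative or fatal bleeds. Suppose the bleeds now counted occur at 3%, a further share q is not counted, and the 3% reference is kept. The probability of declaring infeasibility is P(X ≥ threshold), with X binomial at rate 3% + q.

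| n (threshold) | extra bleeds not counted | q = 1%, counted | q = 2%, counted | q = 3%, counted |
|---|---|---|---|---|
| 515 (23) | 4% | 32% | 74% | 95% |
| 376 (18) | 4% | 25% | 61% | 87% |

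**5. Sensitivity to the reference**

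A wider event may call for a higher reference. At n = 515 a reference of 3.5% needs 26 events and one of 4% needs 29, against 23 at 3%. The table in step 4 therefore shows what happens if the event is widened and the reference is left alone. It does not predict the trial's result.

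**The case against.** The strongest reply concerns timing. The expected-rate sentence in 9.4 adds a parenthesis about hemostasis in the operating room. A patient bleeding mid-operation is already there, so the qualifier may be meant to include a return to theatre, as 5.1.6.4 describes explicitly. The 9.1 table and the 5.2.6 footnote set no time limit, and the five interim bleeds are reported without one. A reader might infer from the final-analysis sentence that all postoperative haemorrhage is definitely excluded. The documents do not support that as fact; they support two readings. This part of the objection stands, and it makes the timing issue a conflict to reconcile. It does not help with grade 5, which no wording includes.

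Second, fatal bleeds are not invisible. Grade 5 events need an expedited report, toxicity is tabulated by arm, and the DSMC reviews safety twice a year. That is true, but none of these feeds the feasibility count.

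Third, three stronger inferences should be set aside:

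- That a surgeon or site with delayed bleeds would look better. The 9.4 rule is a single pooled percentage, and the institution rule in 5.1.6.4 counts postoperative bleeding explicitly.
- That the interim data already sit at the infeasibility boundary. The lower-limit rule belongs to the final analysis; at 59 patients the rule was 13 combined events, and 7 were seen.
- That a particular number of omitted bleeds would reverse the verdict. The documents do not split bleeds by timing, and the 3% was set for the existing wording.

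**Conclusion.** The point holds in two parts of unequal strength. The grade ceiling is firm: under every statement of the rule, a fatal bleed is left out of the numerator that can declare transoral surgery infeasible. The timing part is a contradiction between 9.1, 9.4 and 5.2.6 on a primary decision rule; on the literal wording of the final-analysis sentence, postoperative bleeds are also omitted.

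The decision turns at 23 of 515 or 18 of 376 events with a 3% reference, so a few uncounted events could matter. That rests on exact limits, on the assumed denominators, and on keeping the 3%. With no documented rate for omitted bleeds, and none for grade 5 bleeding alone, an actual effect on the verdict cannot be shown. The plan should be corrected before the final analysis.

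**What to change.** In 9.1 and 9.4, use one definition, counted once per patient: bleeding of grade 3 or higher, including grade 5, intraoperative or postoperative, within one fixed window from surgery that is the same for all patients (30 days, for example). Apply it to the final analysis.

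State whether the expected 3% refers to this definition. If it does not, restate the reference from the source originally used for it, and not from trial data, since five bleeds have already been seen at the interim. If the reference cannot be restated, the fallback is to report intraoperative-only and all bleeds side by side, each with its 90% interval.

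The cost is an amendment to the wording and a recount of adverse-event data that the protocol already collects. The study calendar schedules routine adverse-event evaluation in the first postoperative week and next at completion of treatment, so later bleeds within the window may have to be traced through expedited reports. The downside is that the observed rate can only rise, so widening the event without confirming the reference would tilt the rule towards infeasibility.

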## 9.5 Secondary Objectives

Secondary endpoints include toxicity, overall survival, swallowing function, and patient-reported outcomes.

*Toxicity.* For each arm, all treated patients (regardless of eligibility) will be evaluated by CTCAE version 4.0. Descriptive statistics will be provided (by arm). Difference between the low-dose RT arm (Arm B and Arm C separately) and Arm D and between Arm B and Arm C will be evaluated using Fisher's exact test.

*Overall Survival.* Overall survival will be determined as the time from registration onto the study until death from any cause. Patients who were alive at the time of analysis will be censored at the date last known alive. Kaplan-Meier estimates will be calculated, along with their corresponding 95% confidence intervals. The median, 1-year, and 2-year survival rates will be estimated. Only eligible and treated patients will be analyzed for overall survival (by arm).

*Swallowing Function and Voice.* Descriptive statistics will be provided (by arm) for swallowing function, evaluated using the MBS ratings, PSS-HN normalcy of diet scale, and the validated survey MDADI instrument. Longitudinal analysis will be performed, by arm, on each of these measures. All eligible and treated patients (on both steps) will be analyzed for PSS-HN diet scale, MDADI, and VHI-10. The MBS analysis will be performed on eligible and treated patients only if accrued at vetted participating centers.

*Quality of Life.* The primary variable of interest in the QOL analysis is the individual change in the FACT-H&N total score from baseline (prior to TOS) to 6 months post-RT. Patient QOL will be grouped as "improved" (change  $\geq 7$  points, 6 mo post-RT vs. baseline), "worsened" (change  $\leq -7$  points) and "stable" ( $-6 \leq \text{change} \leq 6$ ). QOL data is very limited in this setting (P16+ OPSCC patients treated with TOS + RT), and estimates from this phase II trial may serve as the basis of choosing an effect size in a possible future phase III trial comparing TOS + RT vs. primary CRT treatment.

In the primary QOL analysis, we plan to combine the post-operative RT arms (B & C) and compare to patients selected for post-operative chemoRT (arm D), which would be expected to have toxicity similar to, but less severe than, a primary CRT approach. This comparison is most similar to the setting of a possible future phase III trial. From a prior trial of CRT approach, about 25% of the patients had improved FACT-H&N from baseline to 6 months, 25% were stable, and 50% worsened, which is expected to be similar to, or slightly worse than the experience of arm D in this phase II trial. Given the more severe overall toxicity and probable greater late toxicity associated with the use of both radiation and chemotherapy, we hypothesize that a higher proportion of patients in arm B/C will have recovered their FACT-H&N scores to baseline level or higher at 6 months, and we consider a difference, or Delta, of 10% (Arms B/C vs. Arm D) to be important outcome. Comparison between Arm B and Arm C (in mean score change and/or proportion of patients with improved/stable score at 6 months) is also important endpoint but this will be only exploratory. Any comparison results will be interpreted with caution. Descriptive statistics will be provided for FACT-H&N and MDASI-HN at various measurement points.

The table below shows the power of detecting various Delta value (Arms B/C vs. D) under various compliance rate (the proportion of patients who complete PRO surveys at both baseline and 6 months post-RT visits), using a one-sided Fisher's exact test with type I error rate of 0.10, assuming 48% intermediate risk patients and 32% high risk patients among evaluable patients.

Compliance Rate	No. of analyzable pts (Arms B/C vs. Arm D)	Delta (Arms B/C vs. D)		
		10% (65% vs. 55%)	15% (70% vs. 55%)	20% (75% vs. 55%)
40%	120 (72 vs. 48)	0.35	0.58	0.79
60%	180 (108 vs. 72)	0.46	0.73	0.91
80%	240 (144 vs. 96)	0.56	0.83	0.96

One of the randomized arms is likely to be selected for a future phase III study. Although the QOL endpoint is not built into the primary selection criteria, in case that the efficacy outcomes for the two randomized arms are similar, the 50Gy schedule will be considered in the phase III study with the expectation that QOL will also be better in this arm, unless there is evidence otherwise.

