4.2.4 Stratification and Classification Factors

4.2.4.1 Classification Factors

- The highest risk feature assessed pathologically will determine the patient's category/treatment arm assignment.
  - Low Risk: T1-T2, N0-N1, with clear ( $\geq 3$ mm) margins, and without any ECE or PNI/LVI.
  - High Risk: Any T stage with positive margin(s), meaning tumor at the specimen edge, not superceded by an additional, tumor free margin, OR "Extensive" ( $> 1$ mm) ECE, OR  $\geq 5$  metastatic

Rev. 7/13

Rev. 2/15

Rev. 6/14

Rev. 1/16

lymph nodes, regardless of primary tumor margin status.

- Intermediate Risk: Any T stage with one or more “close” (<3mm) margin(s) OR “Minimal” (≤ 1mm) ECE, OR 1 or more lymph node >3cm in diameter (N2a neck disease), OR 2-4 lymph nodes positive, any diameter ≤ 6cm (N2b neck disease (regardless of primary tumor margin status)], OR with perineural invasion or lymphovascular invasion.
- Unknown Risk: Pathologic N2c (bilateral nodes), OR Pathologic N3 (> 6cm node)

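### The Arms B+C versus D quality-of-life comparison is powered on a dichotomised FACT-H&N change with an unadjusted Fisher test, giving up power that a baseline-adjusted mean comparison would recover

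*Combined protocol and SAP*

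**What the plan says.** Section 9.5 (Quality of Life) opens: "The primary variable of interest in the QOL analysis is the individual change in the FACT-H&N total score from baseline", measured before surgery and again at 6 months after radiotherapy. It then sorts patients into three groups: improved (gain of at least 7 points), worsened (loss of at least 7 points) and stable (between).

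For the primary QOL analysis, "we plan to combine the post-operative RT arms (B & C) and compare to patients selected for post-operative chemoRT (arm D"). These groups are not randomised. Section 4.2.4.1 states: "The highest risk feature assessed pathologically will determine the patient's category/treatment arm assignment". Only B versus C is randomised, stratified by smoking (Section 4.2.4.2, listed for intermediate risk).

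On effect size, Section 9.5 states: "we consider a difference, or Delta, of 10% (Arms B/C vs. Arm D) to be important outcome". The power table takes 55% in Arm D against 65%, 70% or 75% in B/C, "using a one-sided Fisher's exact test with type I error rate of 0.10". The reference is a prior chemoradiotherapy trial with 25% improved, 25% stable and 50% worsened. The natural reading is therefore that the tabulated proportion is improved or stable, which is a cut at -7 points.

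No covariate is named for B+C versus D. Mean score change is mentioned for B versus C, as an exploratory comparison. Section 9.5 also promises descriptive statistics for FACT-H&N and caution in interpreting comparisons. Section 9.6 deals with missing data, not covariate adjustment.

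**The concern.** Reducing a continuous score to a yes/no outcome discards information, and Fisher's exact test then adds its own conservatism. The plan accepts power of roughly one third to just over one half for a difference it regards as important. It does so although every analysable patient has both scores needed for a more efficient analysis: the table defines compliance as completing both the baseline and the 6-month survey.

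Section 9.5 says that the QOL estimates may help to choose an effect size for a possible phase III trial. It also says that, if efficacy is similar, the 50 Gy schedule will be considered on the expectation of better QOL unless there is evidence otherwise. An imprecise QOL analysis is poorly placed to supply either the effect size or that evidence.

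**Working it through.** **Inputs from Section 9.5.** Proportions 0.65 (B/C) and 0.55 (D); one-sided alpha 0.10; analysable patients 72 vs 48, 108 vs 72 and 144 vs 96 at 40%, 60% and 80% compliance.

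**Step 1: reproduce the plan's figures.** Exact power of the one-sided Fisher test is the sum of the two binomial distributions over the hypergeometric rejection region. For 10 percentage points it gives 0.353, 0.464 and 0.556, against the stated 0.35, 0.46 and 0.56. The other six cells also reproduce. The table is arithmetically correct.

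**Step 2: Fisher conservatism.** With both proportions at 0.55, the test's true size is 0.072, 0.076 and 0.080, not 0.10. A normal-approximation two-proportion test on the same dichotomy has power 0.428, 0.526 and 0.608. The differences are 0.428 - 0.353 = 0.075, 0.526 - 0.464 = 0.062 and 0.608 - 0.556 = 0.052. So about 5 to 7.5 percentage points of power are lost to the test, not to the dichotomy.

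**Step 3: the same difference on the continuous scale.** Assume normal change scores with equal SD and a pure location shift:

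d = z(0.65) - z(0.55) = 0.385 - 0.126 = 0.26 SD of change.

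The documents state no SD. Under normality the 25/25/50 split implies about 13/0.674 = 19 to 14/0.674 = 21 points, depending on how the gap between categories is treated. On that basis 0.26 SD is about 5 FACT-H&N points.

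**Step 4: unadjusted comparison of mean change.**

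Power = Φ(d·√(n1·n2/(n1+n2)) - 1.2816)

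- 72 vs 48: Φ(0.26 × 5.37 - 1.28) = 0.54
- 108 vs 72: Φ(0.26 × 6.57 - 1.28) = 0.66
- 144 vs 96: Φ(0.26 × 7.59 - 1.28) = 0.75

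A noncentral t calculation gives 0.543, 0.663 and 0.754.

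**Step 5: ANCOVA with baseline as covariate.** Let r be the within-group correlation of baseline and 6-month scores, with equal variances at the two times and no baseline difference between groups. The change score has variance 2σ²(1 - r) and the ANCOVA residual has variance σ²(1 - r²). The standardised effect is therefore multiplied by √(2(1 - r)/(1 - r²)) = √(2/(1 + r)).

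- r = 0.7: multiplier 1.085; power at 144 vs 96 is 0.80, at 72 vs 48 it is 0.59
- r = 0.4: multiplier 1.195; power at 144 vs 96 is 0.86, at 72 vs 48 it is 0.65

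| Analysable (B/C vs D) | Fisher (plan) | Normal approx., same dichotomy | Mean change | ANCOVA, r 0.7 to 0.4 |
|---|---|---|---|---|
| 72 vs 48 | 0.35 | 0.43 | 0.54 | 0.59 to 0.65 |
| 108 vs 72 | 0.46 | 0.53 | 0.66 | not needed for the conclusion |
| 144 vs 96 | 0.56 | 0.61 | 0.75 | 0.80 to 0.86 |

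The unadjusted gain over Fisher is about 19 to 20 percentage points. Of that, 5 to 7.5 points come from Step 2; the remainder is the cost of dichotomising.

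**The case against.** The case for leaving the plan alone has real substance.

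- **Baseline is used.** A reader might infer that the plan ignores the baseline score. It does not: the endpoint is "the individual change in the FACT-H&N total score from baseline (prior to TOS) to 6 months post-RT". What is missing is baseline as a covariate.
- **Continuous summaries are promised.** A reader might infer that the trial cannot supply a mean and SD for phase III planning. The promised descriptive FACT-H&N statistics, and mean score change for B versus C, contradict that. What is not specified is an adjusted mean difference with its CI.
- **Baseline imbalance is not shown.** Baseline is measured before surgery, and Arm D is defined afterwards by pathology. Eligibility limits everyone to cT1-T2, cN1-N2b and performance status 0-1, and Appendix X describes enrolled patients as not distinguishable before operation. The documents do not support a claim that baseline QOL differs by later risk group. The argument here rests on precision.
- **ANCOVA does not cure confounding.** Pathology alone separates B/C from D, with no overlap. In non-randomised groups, ANCOVA and change-score analyses can also disagree.
- **The final test is not fixed.** Fisher's test appears in the power paragraph, and no sentence commits the final analysis to it. That is itself a gap.
- **Responder categories have value.** They are interpretable and match the only reference data the plan has.
- **The stakes are limited.** This is a secondary phase II endpoint outside the primary selection criteria. The low power is openly tabulated and caution is promised.

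All of these points stand as limits. None of them recovers the lost power or gives a reason to leave baseline out of the model.

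**Conclusion.** The concern holds in a bounded form. The plan names a continuous QOL variable but powers its main QOL comparison on a dichotomy, with a conservative exact test and no covariate. Its own table shows power of 0.35 to 0.56 for the difference it calls important. Comparing mean change would raise this to about 0.54 to 0.75, and ANCOVA at 144 versus 96 to about 0.80 to 0.86.

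The size of the gain depends on normality, a pure location shift and, for ANCOVA, assumed correlations of 0.4 to 0.7 with equal variances and no baseline difference. None of these is given in the documents. The power table contains no error, and nothing here shows that the B+C versus D result would be biased by baseline imbalance.

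The case is strongest for B versus C. That comparison is randomised, mean score change is already contemplated, and adjusting for baseline and the stratification factor has no real downside. For B+C versus D, adjustment improves precision, but the contrast stays confounded by pathologic risk.

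**What to change.** 1. **B versus C.** Analyse the 6-month FACT-H&N score by ANCOVA with baseline FACT-H&N and the smoking stratum as covariates, and report the adjusted mean difference with its CI. Restrict this to randomised patients, because Arm C also takes pN2c/N3 patients by direct assignment (Section 5.1.8.4).
2. **B+C versus D.** Prespecify an ANCOVA of the 6-month score on group and baseline FACT-H&N. Report the adjusted mean difference with its CI alongside the unadjusted mean change. Label the contrast non-randomised and still confounded by pathologic risk. Add smoking only if it is recorded for Arm D; Section 4.2.4.2 lists it as a stratification factor for intermediate risk only.
3. **Responder proportions.** Keep reporting improved, stable and worsened, so that the link to the 25/25/50 reference data is retained.

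The cost is SAP wording and the regressions. FACT-H&N is already scheduled at baseline and at 6 months after radiotherapy (Appendix V), so no new QOL data are needed. The downside is that the headline moves from a responder proportion to a mean difference. For the non-randomised contrast, the ANCOVA and change-score results may differ, which is why both should be shown.
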